***The following documents are currently attached to this item:***

Subject recruitment (03.15.2019\_flyer\_initialsubmission.docx)

**Subject compensation\***

Will subjects be financially compensated for their participation?

Yes

***The following documents are currently attached to this item:***

*There are no documents attached for this item.*

***If there is subject compensation, provide the schedule for compensation per study visit or session and total amount for entire participation, either as text or separate document***

Total compensation for completing all study visits is \$720.00. Subjects will receive additional compensation (\$0.17-\$150) depending on the choices they make during the incentive-based tasks of the Neuromodulation Sessions. We will explain the details of the compensation before they begin the task. Subjects will receive compensation at the end of their study completion. If subjects do not fully complete the study, they will receive compensation for the parts of the study they did complete, based on the following outline: Visit 1: Clinical Interview (\$20.00) Visit 2: Baseline MRI (\$50.00) Visit 3 TMS/fMRI (\$150.00) Visit 4-6: 1st Neuromodulation Session (\$50.00 x 3 = \$150.00) Visit 7: TMS/ fMRI (\$100.00) Visit 8-10: 2nd Neuromodulation Session (\$50.00 x 3 = \$150.00) Visit 11: TMS/fMRI (\$100.00). Subjects will be compensated through University of Pennsylvania supported Greenphire ClinCard. This is a reloadable virtual or physical prepaid card (similar to a debit/credit card) which allows funds to be available immediately. Study staff will provide participants with a ClinCard Cardholder FAQ: US document (attached). Subjects who do not feel comfortable with the Greenphire ClinCard may be compensated by a check, in lieu of the ClinCard. We are not stating this option in the ICF, as we would prefer all participants to use the ClinCard for consistency; however, we acknowledge that not all individuals will feel comfortable with this method and therefore, if a participant expresses discomfort, we will then verbally offer them the option of being paid with a check. If participants opt to have the payment provided to them in the form of a check; it will be mailed to their home address. Participants will be required to complete an electronic C-2 and a W-9, including providing their full social security number, in order to receive the study payment. If participants choose to participate in multiple studies at the center, some similar/identical study visits (mainly screening visit and baseline MRI) may not need to be repeated. If this is the case, participants will only be compensated for the new study procedures/visits they complete.

# Study Procedures

## Suicidal Ideation and Behavior

Does this research qualify as a clinical investigation that will utilize a test article (ie- drug or biological) which may carry a potential for central nervous system (CNS) effect(s)? Central nervous system(CNS) effect: the ability of a test article to enter into and potentially interact with the central nervous system (brain and spinal cord). Clinical Investigation: Any experiment that involves a test article and one or more human subjects that either is subject to requirements for prior submission to the Food and Drug Administration (FDA) under section 505(i) or 520(g) of the Federal Food, Drug, and Cosmetic Act, or is not subject to the requirements for prior submission to the FDA under these sections of the act, but, the results of which are intended to be submitted later to, or held for inspection by, the FDA as part of an application for a research or marketing permit.

No

## Procedures

All participants will be recruited through the University of Pennsylvania and the surrounding community. Subjects will be pre-screened for eligibility through phone or online self-report screener in REDCap. Eligible subjects will be invited in for a screening visit. Visit 1 will be a consent/ screening session. This visit will involve remote and in-person procedures. During the remote visit, a coordinator will discuss the Informed Consent Form with the participant. After going through the ICF, participants will be asked to electronically sign at the end of the ICF and complete a Remote ICF Attestation form to ensure they understood all the procedures and risk associated with the study. If they agree to participate, they will complete questionnaires related to their medical history, demographics, and eligibility to receive MRI scans and TMS. After completing the questionnaires, participants will undergo a clinical interview. This interview could be done in person or remote. If participants meet eligibility for these initial procedures, we will schedule an in-person meeting to test TMS. For the TMS demo, participants will receive several short rounds of TMS test pulses to the prefrontal cortex to ensure comfort. During this demonstration we will identify the participants resting motor threshold (MT). MT is defined as the minimum magnetic flux needed to elicit a response in a target muscle in 5 out of 10 trials. MT is the standard in the field for measuring cortical excitability and to reduce seizure risk. While TMS is usually quite tolerable, a minority of participants (20%) cannot tolerate stimulation procedures. Screening data will be recorded in REDCap; this data will be retained indefinitely until the study enrollment is completed. The information collected in this initial visit will determine if the subject meets all inclusion criteria. If participants screen-fail or withdraw, we will assign the clinical interview compensation to their virtual Greenphire Clincard. Upon meeting all criteria for inclusion in the study, subjects will then return to complete a 1-hour baseline MRI scan at Visit 2. All MRI imaging protocols will be reviewed and approved by CAMRIS. An experienced technician and a member of the study team will be present during the MR session to ensure participant safety and well-being. If the participant complains of feeling claustrophobic and does not wish to complete the MRI, the study will be terminated. Emergency personnel and equipment are immediately available to the MRI room should the need arise. It is possible that during the course of the research study, the research staff may notice unexpected findings on an MRI scan. Should this occur, the findings will be assessed by a trained radiologist. The study doctor will inform research subjects of any significant findings. Visit 3 will include fMRI and interleaved TMS/fMRI. During this scan, the participant will perform a working memory N-back task several times. Brain data from the baseline MRI scan (stimulation target in individualized brain space) will be calibrated with the skin and scalp using a Polaris Vicra camera (Brainsight neuronavigation) to allow marking of the stimulation site on a swim cap for the TMS/fMRI session. During the MRI scan, participants will receive interleaved TMS/fMRI probes to the brain targets. The purpose of this TMS/fMRI scan is to probe and modulate and measure activity in targeted neural circuits following our established methods (Chen et al., 2013). Moreover, by building brain decoding models using LSTM RNNs deep-learning technique, we can establish a closed loop of rTMS and brain readouts. As a result, we will be able to fine-tune the rTMS frequency to achieve optimal brain state and maximized working memory performance during this session. Our MRI-compatible TMS system (MagPro X100 Stimulator, MRI-B91 TMS coil) is housed in Stellar Chance (SC3T) and the Hospital of the University of Pennsylvania (HUP 6) at the 3-Tesla MRI machine. The apparatus was installed under the supervision of [name]. a member of CAMRIS. TMS in an MRI scanner involves no additional risks to the subject. Visits 4-6 will involve excitatory rTMS delivered in the

same interleaved pattern at the same stimulation site as the TMS/fMRI session but with either the optimized frequency determined from that session or the frequency least successful in moving their brain state (half of the participants will receive optimized stimulation frequency, and the other half of the participants will receive least-optimized stimulation frequency during these sessions). The present study utilizes the same FDA-approved devices (Magventure Cool-Coil B65, MagVenture X100 Stimulator) to administer TMS. The TMS system is housed in the Richards Biomedical Building. Only individuals trained by the Principal Investigator ([name].) and, [name] (M.D.) will dispense TMS. In addition to receiving TMS, participants will complete questionnaires and computerized tasks during these visits. The tasks will assess reaction time, working memory, decision-making. The decision-making task will be incentive-based and the amount the participant earns will be added to their final study compensation. During some of the tasks, we may ask subjects to wear a passive eye-tracking device to record the location of your gaze at any particular time. The order of tasks will be randomized for each participant. Visit 7 will involve a 1-hour TMS/fMRI session. Participants will complete the working memory N-back task while inside the scanner. The purpose of this visit is to examine the brain and behavioral changes after the first round of neuromodulation. Visit 8-10 will mirror Visit 4-6 and will involve neuromodulation with either the optimized or least-optimized individual frequency. The order of optimized and least-optimized frequencies will be counterbalanced across participants between Visit 4-6 and Visit 8-10 (i.e., half of the participants will receive stimulations of the two frequencies in one order, and the other half will receive stimulations of the two frequencies in the reverse order). Visit 7 and the Visit 8 will be scheduled at least one week apart. In addition, unless the MRI is unavailable or we encounter scheduling constraints, Visit #3-Visit #7 will be scheduled within the same work week, such as Visit #3 is on Monday, Visits #4-7 are Tuesday/ Wednesday/Thursday, respectively, and Visit #7 is on Friday. Similarly, Visit #8-Visit #10 will be scheduled 4 work-days in a row, either Monday-Thursday or Tuesday-Friday. Visit 11 will mirror Visit 7 and examine brain and behavioral changes after the second round of neuromodulation. Monitoring will include: (1) successful recruitment, retention; (2) subject adherence; (3) safety and tolerability.

**The following documents are currently attached to this item:**

*There are no documents attached for this item.*

**Deception**

Does your project use deception? Deception could be considered any direct misinformation presented to the subject or omission of key information pertaining to the design or nature of the project.

No

**International Research**

Are you conducting research outside of the United States?

No

**Analysis Plan**

For the primary within-subjects analyses, a time (pre vs post rTMS) by condition (optimized vs least-optimized frequency) ANOVA will be done both on task performance as well as fMRI voxelwise brain responses.

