### **Design**

This study will recruit 38 healthy participants, who will be recruited through the community via study advertisements. Prior to any study visits, all subjects will be pre-screened through a phone interview with a trained member of the study team or an online self-report screening, both through REDCap. The study involves 11 study visits. The first study visit will consist of a consenting and extended screening visit. All participants will have the opportunity to ask questions before signing the electronic consent form. We will complete a semi-structured clinical interview and will demonstrate TMS to ensure the participant is comfortable with all study procedures. This visit will be completed both remote and in- person. The second study visit will involve a 1-hour MRI scan. During the scan, the participant will complete multiple computerized tasks. The MRI scan will include both structural and functional scans, and those scans will be used to localize the stimulation target for the subsequent sessions. The third study visit will be a 2-hour TMS/fMRI session, and the participant will engage in behavioral tasks while interleaved rTMS rounds are delivered at different excitatory frequencies (frequency range: 2Hz-20Hz). This scan will be used to determine the optimal stimulation frequency for the individual participant. The fourth, fifth, and sixth study visits will involve neuromodulation with either the optimized frequency or the frequency least successful in moving a participants brain state, as determined from the third study visit. Each subject will receive ~3000 pulses in each session, including the pulses from the motor threshold determination. We will determine the adjusted MT by using the Stokes equation, which accounts for differences in cortical distance from the site relative to motor cortex (where the motor threshold is found). The stimulation amplitude will be equivalent to 110% of the adjusted MT. Prior studies have safely utilized TMS with such design (VanDerwerker et al., 2018; Cristancho, Trapp, Siddiqi, Dixon, & Lenze, 2018). The seventh study visit will involve a 1-hour TMS/fMRI session while the participant is engaging in a behavioral task.. This visit is designed to examine brain and behavioral changes after the first round of neuromodulation. The seventh and the eighth visit will be scheduled at least one week apart. The eighth, ninth, and tenth study visits will mirror the fourth, fifth, and sixth study visits and will involve neuromodulation with either the optimized or least-optimized individual frequency. The order of optimized and least-optimized frequencies will be counterbalanced across participants between Visit 4-6 and Visit 8-10 (i.e., half of the participants will receive stimulations of the two frequencies in one order, and the other half will receive stimulations of the two frequencies in the reverse order). The

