#### **Accrual**

All recruitment will be conducted through the University of Pennsylvania and the surrounding community to find a total of 38 healthy participants. It is assumed that there will be some participants who screen fail, are lost to follow up, withdraw, or complete without usable scanner data. Therefore, we estimate that we will need to consent/enroll up to 38 participants overall, in order to adequately test the hypotheses on at least 28 participants.

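### The primary time by condition ANOVA has no period term for a two-round counterbalanced crossover, so a shift between rounds inflates the error and, if the analysed orders are unequal, biases the frequency effect

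*Combined protocol and SAP*

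**What the plan says.** The Analysis Plan is one sentence. It reads "For the primary within-subjects analyses, a time (pre vs post rTMS) by condition (optimized vs least-optimized frequency) ANOVA will be done" and applies the model "both on task performance as well as fMRI voxelwise brain responses". Time and condition are the only factors named.

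The Design section describes a two-period, two-sequence crossover, in which "half of the participants will receive stimulations of the two frequencies in one order, and the other half will receive stimulations" in the reverse order. Round 1 is Visits 4-6 with a post-round scan at Visit 7. Round 2 is Visits 8-10 with a post-round scan at Visit 11. Visits 7 and 8 are at least one week apart.

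The two rounds do not have the same lead-in:

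- At Visit 3, "the participant will engage in behavioral tasks while interleaved rTMS rounds are delivered at different excitatory frequencies". The Procedures section adds: "During this scan, the participant will perform a working memory N-back task several times".
- Barring scheduling constraints, "Visit #3-Visit #7 will be scheduled within the same work week", so round 1 directly follows that session. No such session is listed before round 2.
- At Visit 7, "Participants will complete the working memory N-back task while inside the scanner", and Visit 11 mirrors Visit 7. Working memory is also among the abilities tested at Visits 4-6, which Visits 8-10 mirror.

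The Accrual section plans up to 38 enrolled to obtain at least 28 for analysis: "It is assumed that there will be some participants who screen fail, are lost to follow up, withdraw", or finish without usable scanner data. The documents do not say when order is assigned, which measurement is the pre value for round 2, or how unequal analysed orders would be handled.

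**The concern.** Counterbalancing protects the average frequency effect from a shift between rounds only if the two orders are equal in the analysed set. It never removes the shift from the error term. That takes a period term, and the plan has none.

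A shift is plausible here. The same task recurs across visits, and only round 1 is planned for the same work week as a multi-frequency stimulation session. The first feature bears on task performance. The second could also affect the brain readouts at rest. At stake is avoidable loss of power in a study of about 28 analysable participants. If losses fall unevenly on the two orders, part of the shift would also be reported as a frequency effect.

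**Working it through.** The plan gives no alpha, power, effect size or SD, so there is no stated figure to reproduce.

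**Inputs from the documents.** Analysed n = 28; enrolled up to 38; two orders, planned 1:1; model with time and condition only.

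**Assumptions.** Two-sided alpha 0.05; no carryover; a true effect of 0.549 SD of the paired difference (80% power in a paired t test at n = 28 when P = 0); P from 0.25 to 1.0 of that SD.

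**Step 1: what the planned test is.** In a 2 x 2 within-subject ANOVA, the time x condition test is the paired t test (27 df) on d = change(optimized) - change(least-optimized).

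**Step 2: how P enters.** Let P be the round 2 minus round 1 difference in pre-to-post change that is not due to frequency. Then d = effect + sP + error, with s = +1 if optimized comes second and -1 if it comes first. With order sizes n1 and n2 and P in SD units:

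- Bias = P(n1 - n2)/n.
- Error variance is multiplied by 1 + P²[1 - ((n1 - n2)/n)²] x n/(n - 1).

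At 14/14 and P = 0.5 the bias is 0 and the multiplier is 1 + 0.25 x 28/27 = 1.26.

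**Step 3: can P be taken as zero?** Let g1 be the practice gain from Visit 3 to Visit 7, and g2 the gain from Visit 7 to Visit 11.

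- Visit 3 as common pre: P = (g1 + g2) - g1 = g2, which is zero only if learning is complete by Visit 7.
- Visit 7 as the second pre: P = g2 - g1, which is zero only if practice is linear.

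Neither reading makes P zero in general.

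**Step 4: equal orders (14/14).** Effective n is approximately 28/(1 + P²).

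| P (SD) | Error variance multiplier | Effective n | Type I error, planned | Power, planned | Power, period term |
|---|---|---|---|---|---|
| 0.25 | 1.07 | 26 | 4.4% | 78% | 79.9% |
| 0.5 | 1.26 | 22 | 2.9% | 72% | 79.9% |
| 0.75 | 1.58 | 18 | 1.5% | 63% | 79.9% |
| 1.0 | 2.04 | 14 | 0.6% | 50% | 79.9% |

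The planned-test columns are simulated. The last column is exact noncentral-t power on 26 df.

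**Step 5: unequal orders.**

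- 15/13: bias 2/28 = 0.07P. At P = 0.5, planned power is 78% or 66% depending on the sign of P, against 79.7% with the term.
- 16/12: bias 4/28 = 0.14P. At P = 0.5, planned power is 83% or about 60% by sign, against 79.1% with the term. The 83% is not a gain, because it comes from the bias. Type I error is 4.0%, 3.0% and 2.2% at P = 0.5, 0.75 and 1.0.
- 18/10: bias 8/28 = 0.29P. Type I error is 7.6% to 10.3% over P = 0.5 to 1.0.

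**Step 6: how likely is imbalance?** If 28 remain at random from equal orders (hypergeometric), the chance of a gap of 4 or more is 27% from 19/19, 17% from 17/17, 10% from 16/16 and 0 from 15/15. A gap of 8 or more has probability 0.8% from 19/19 and 0 from 17/17 or fewer.

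**Step 7: which term removes P?** Take pre and post rows without noise, no frequency effect, orders 16/12, g1 = 1, g2 = 0.3 and Visit 7 as second pre. Then |P| = 0.7 and the spurious time x condition estimate should have size 0.7 x 4/28 = 0.10. It is 0.10 with time and condition, still 0.10 after adding period and sequence main effects, and 0.00 after adding time x period.

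**The case against.** The strongest reply is that the planned test stays valid in most realistic cases and that the size of the problem rests on an assumed P.

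- **Size of P.** P is not the practice effect itself but a later gain or a difference between gains. By Visit 7 participants have done N-back several times and other working-memory testing, so P may be small. At 0.1 SD and 14/14 the power loss is negligible, and at 0.25 SD it is about two points. The 63% and 50% figures need shifts that nothing in the documents supports directly. This stands, and it is why a range is shown.
- **Bias.** The Procedures section says 20% cannot tolerate stimulation and places the TMS demonstration at Visit 1, and Accrual counts screen failures within the 38. On that rate about 8 of the 38 (0.20 x 38 = 7.6) would leave at screening. If order is assigned afterwards, about 30 remain (15/15), and the worst split at n = 28 is 15/13 with bias 0.07P. This also stands. The 19/19 start is the upper end, and the 18/10 split should carry little weight. The time of assignment is not stated, so larger gaps cannot be excluded.
- **The pre measurement.** Visit 2, called the baseline MRI, or tasks within the neuromodulation visits could also serve as pre. A common Visit 2 pre still leaves P = g2. Within-visit measurement would make P the between-round difference in within-visit change. The definition is needed first in any case.
- **Brain endpoint.** The figures are for one univariate test at 5%. The algebra holds at each voxel, but the power figures do not carry over to a voxelwise threshold, which the plan does not state.

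None of this supplies the missing term or gives a reason to leave it out.

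**Conclusion.** The concern holds. The design has two periods and two orders, the model has neither, and no other section adds them. The main consequence is a conservative test. At 14/14 the loss is about 2 points of power at P = 0.25 SD, 7 to 8 at 0.5 SD and 30 at 1.0 SD, from a reference of 80%. Bias arises only with unequal analysed orders and is 0.07P at 15/13 and 0.14P at 16/12. Type I error above 5% needs a rare split such as 18/10 and is not the main issue.

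The existence of the problem follows from algebra. Its size rests on the assumed P, effect size and alpha, and the chance of imbalance depends on when order is assigned. It should be fixed, with medium confidence in how much it matters in practice. A period term does not deal with carryover, which is a separate question.

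**What to change.** 1. Define the pre measurement for each round.
2. Analyse the pre-to-post change per round in a linear mixed model with fixed effects for condition, period (round 1 or 2) and sequence (order group), and a random participant effect. With complete data, the same condition test comes from averaging the two order-group means of the paired difference of changes, using the pooled within-order variance.
3. If pre and post rows are both modelled, include time x condition together with time x period. A period main effect alone does not remove P, and neither does a sequence main effect.
4. Apply the same structure to N-back performance and to the brain endpoint. The mixed model can also keep participants with only one usable post scan. That is a secondary benefit, and its value was not computed here.

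The cost is a short rewrite of the Analysis Plan and no new data. If P is in fact zero, power goes from 80.0% to 79.9% at 14/14 and to 79.1% at 16/12.

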### **Secondary outcome variable(s)**

Correlation between changes in behavioral measures and changes in network connectivity before and after the neuromodulation.

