#### **Study duration**

Each subject will spend a total of approximately 13.5-20 hours of participation in the study over 11 study sessions. The study schedule is as follows: Visit 1: Consent/Screening (1-3 hours) Visit 2: Baseline MRI (1.5-2 hours) Visit 3: TMS/fMRI (2-2.5 hours) Visit 4-6: 1st Neuromodulation Session (1-1.5 hours each) Visit 7: TMS/fMRI (1.5-2 hours) Visit 8-10: 2nd Neuromodulation Session (1-1.5 hours each) Visit 11: TMS/fMRI (1.5-2 hours).

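### The primary time-by-condition ANOVA carries no period term for a counterbalanced two-period design and, for fMRI, does not name the 'pre' scan of the second condition

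*Combined protocol and SAP*

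**What the plan says.** The Analysis Plan section gives the primary within-subject analysis in a single sentence: "a time (pre vs post rTMS) by condition (optimized vs least-optimized frequency) ANOVA will be done", applied to task performance and to voxelwise fMRI responses. Two factors are named. Period, sequence and order are not, and neither is the visit that supplies 'pre' for each condition.

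The visit list under Study duration places imaging at four visits. Two precede both conditions: "Visit 2: Baseline MRI (1.5-2 hours) Visit 3: TMS/fMRI (2-2.5 hours". The other two follow the two rounds of stimulation: "Visit 7: TMS/fMRI (1.5-2 hours) Visit 8-10: 2nd Neuromodulation Session (1-1.5 hours each) Visit 11: TMS/fMRI (1.5-2 hours". The Design section adds that "The seventh and the eighth visit will be scheduled at least one week apart".

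Procedures says that "Visit #3-Visit #7 will be scheduled within the same work week", so round 1 opens and closes with a scan. For round 2 it says "Similarly, Visit #8-Visit #10 will be scheduled 4 work-days in a row". That sentence puts three visits into four days and should be reconciled with the visit list, but it gives round 2 no opening scan. Procedures also states that "The order of optimized and least-optimized frequencies will be counterbalanced across participants between Visit 4-6 and Visit 8-10".

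The secondary outcome is defined from change scores too: "Correlation between changes in behavioral measures and changes in network connectivity before and after the neuromodulation".

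**The concern.** A two-period crossover has three sources of systematic difference between its post-treatment scans: condition, period, and whatever remains of the first round. The plan handles period by counterbalancing the order and then leaves it out of the model. Counterbalancing protects the mean, but not the error term, and it protects the mean only while the usable participants stay balanced across orders.

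Separately, a time-by-condition interaction needs a 'pre' and a 'post' for each condition. For fMRI the second condition has a 'post' (Visit 11) but no scan between the gap and Visit 8. An analyst could use an earlier baseline for both conditions, or use Visit 7 for the second. These are different contrasts that respond differently to incomplete washout. At stake are the power of a small primary test, the clarity of what it estimates, and the definition of the secondary change scores.

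**Working it through.** The plan states no alpha, power, effect size or variance, so there is no figure of its own to reproduce.

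**Inputs from the documents.** Scans at Visits 2, 3, 7 and 11 (Study duration). Two orders, half of participants each (Design, Procedures). At least 28 analysable of up to 38 enrolled (Accrual).

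**Assumptions, not in the documents.** One scalar two-sided 5% test; visit errors with SD 1, independent unless stated; D = true optimized minus least-optimized difference; L = share of the round-1 effect left at Visit 11; s = shift from Visit 7 to Visit 11 unrelated to condition; m = mean response common to both frequencies. Power figures are illustrative and do not carry over directly to a voxelwise map.

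**1. What each choice of 'pre' tests.**
- Shared baseline (Visit 3, say): (V7 − V3) − (V11 − V3) = V7 − V11. The baseline cancels. Averaged over the two orders, the expected value is D(1 − L/2): 1.00D, 0.75D and 0.50D at L = 0, 0.5 and 1. The variance is 2.
- Visit 7 as second 'pre': (V7 − V3) − (V11 − V7) = 2·V7 − V3 − V11. The round-1 after-effect is subtracted from the second condition's change. The expected value is D(3 − L)/2: 1.50D, 1.25D and 1.00D. The variance is 6, so the SE is √3 = 1.73 times as large.

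**2. Omitted period term, shared baseline, 14:14.** The signed difference has mean D − s in one order and D + s in the other. The mean over orders is still D, but the estimated variance becomes about 2 + s²·28/27.
- s = 0.5: variance 2.26, SE overstated by √(2.26/2) = 1.06.
- s = 1: variance 3.04, SE overstated by √(3.04/2) = 1.23.
- At D = 0.8 the noncentrality is 0.8·√28/√2 = 2.99 and the 27-df critical value is 2.05. Power is about Φ(2.99 − 2.05·1.06) = Φ(0.81) = 79%, and Φ(2.99 − 2.05·1.23) = Φ(0.46) = 68%.
- With the period term (26 df) power is 82% at either shift. Simulation gives the same values.
- Simulated type I error without the term is 3.8% at s = 0.5 and 1.7% at s = 1. With the term it is 5%.

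**3. Carryover of a common response acts as a shift.** With V7 − V11 it adds L·m to the order difference. With Visit 7 as 'pre' it adds (1 − L)·m. With D = 0, m = 1 and no period term, simulated type I error is about 1.7% for the shared baseline at L = 1, and about 3.5% for the Visit 7 reading at L = 0. Both are conservative.

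**4. Unequal orders.** The bias is (n₁ − n₂)/(n₁ + n₂) times s in size: 2/28 = 0.07 at 15:13, 4/28 = 0.14 at 16:12, 6/28 = 0.21 at 17:11. At 17:11, s = 1 and D = 0.8, the estimate is 0.59 or 1.01 depending on which order is larger; with the period term it is 0.80. If 38 were allocated 19:19 and 28 were usable at random, 16:12 or worse would occur in 27% and 17:11 or worse in 6%. With fewer allocated after screening, it would occur less often.

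**5. Which reading has more power is not settled.** With independent errors, the ratio of expected z (shared/Visit 7) is √3(2 − L)/(3 − L) = 1.15, 1.04 and 0.87 at L = 0, 0.5 and 1. Visits 3 and 7 normally share a work week, so their errors may correlate. With correlation r between them only, the variance in the Visit 7 reading is 6 − 4r and the ratio is √(3 − 2r)(2 − L)/(3 − L). At r = 0.4 it is 0.99, 0.89 and 0.74. Above r = 0.375 the Visit 7 reading has the higher expected z at every L. At D = 0.8 and r = 0.4, simulated power (shared against Visit 7) is 82 against 83%, 58 against 68%, and 30 against 49%.

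**6. Secondary change scores.** Here 'pre' does not cancel. With a shared baseline the errors of the two rounds' changes correlate at 1/2 = +0.5. With Visit 7 as second 'pre' they correlate at −1/2 = −0.5.

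**The case against.** The strongest reply is that the reading is clear enough. Only Visit 2 is called a baseline, Visit 7 is described as the look after round 1, Visit 11 mirrors it, and nothing gives Visit 7 a 'pre' role. On that reading the interaction is Visit 7 against Visit 11, which is the contrast recommended below. This largely stands: the unnamed 'pre' is mainly a matter of clarification.

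A reader might go further and infer that the primary fMRI test is undefined, or that its type I error is inflated. The documents do not support this. Either reading gives a definite test, and without a period term both err on the conservative side when orders are equal. The error rate rises, to about 7.5% for one scalar test, only if the choice is made after seeing both results, and nothing says that it will be.

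A second reply is that counterbalancing already deals with period. It does so for the mean at equal orders. It does not remove the inflated error, and it does not protect the estimate if losses fall unevenly. The 1-SD shift has no basis in the documents; at 0.5 SD the loss is only about 3 points of power.

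For task performance the missing-scan point does not apply. Working-memory tasks are also given at the neuromodulation visits, so a round-2 'pre' value may exist, although their timing relative to the pulses is not stated.

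**Conclusion.** The point holds as one that should be fixed, not as a fatal flaw. The stated ANOVA leaves out the period structure that the design deliberately creates, and for fMRI it leaves the second condition's 'pre' scan unnamed.

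The period term is the substantive gain. Its omission costs about 3 points of power at a 0.5-SD shift and about 14 at a 1-SD shift, under 14:14, independent errors and D = 0.8. It biases the estimate only when usable orders are unequal, by 0.14 or 0.21 of the shift at 16:12 or 17:11.

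The algebra for the expected contrasts and the bias needs no assumed effect size. The power figures do, and they apply to a single scalar test. It would be tempting to rank the two readings by power, with a crossover at L = 0.63. That threshold comes from step 5 with independent errors and is one scenario only: washout and between-visit correlation are both unknown, and a same-week correlation above 0.375 removes the crossover.

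**What to change.** - Prespecify the primary fMRI contrast as optimized against least-optimized on the post-neuromodulation scans (Visit 7 against Visit 11), in a crossover model with participant, condition and period terms, fitted at each voxel.
- State that it assumes washout over the gap and is attenuated by (1 − L/2) if a share L of the round-1 effect remains. A period term does not repair this, and no scan in the schedule checks it directly.
- Report the version with Visit 7 as second 'pre' only as a labelled sensitivity analysis.
- For task performance, use the same period term and name the visit and time point that serve as 'pre' in each round.
- For the secondary correlation, use one named scan from before round 1 as 'pre' for all change scores.

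The cost is analysis-plan wording and one degree of freedom, with no added scan or visit. With no shift, the period term costs about 2 points of power at 17:11 (82% to 80% at D = 0.8) and almost nothing at 14:14. If washout is poor or same-week errors are well correlated, the recommended contrast may have less power than the sensitivity version.
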